## 2.2 SUBJECT SELECTION

### A. Study Population

To ensure clinically evaluable data from 400 subjects (a minimum of 200 subjects in each of two treatment groups), approximately 450 outpatient subjects with community-acquired pneumonia will be admitted to the study.

### B. Inclusion Criteria

Subjects may be included in the study if they satisfy all of the following criteria:

1. Age: 18 years of age or older
2. Sex: male or female
3. Clinical picture consistent with pneumonia, including at least two of the following clinical signs or symptoms of pneumonia:
  - cough
  - fever (101°F or greater)
  - production of purulent sputum
  - rales
  - pleuritic chest pain
4. Chest x-ray infiltrate compatible with acute infection
5. If female, subject must be using an acceptable form of birth control and have a negative pregnancy test prior to being enrolled; or be post-menopausal
6. Must be able to give informed consent

### C. Exclusion Criteria

1. Subjects infected with a resistant organism known prior to starting therapy
2. Previous allergic or serious adverse reaction to any members of the quinolone class of antimicrobials, or a severe reaction to penicillin or any cephalosporin
3. Severe renal failure (creatinine clearance < 20 ml/min)
4. Presence of neutropenia (< 500 WBC's/mm^3)
5. Pregnant women or nursing mothers
6. Use of an investigational agent within 30 days prior to entry into the study
7. Previous treatment under this protocol

## **D. Patient Recruitment and Screening Procedures**

Subjects who meet all the inclusion criteria and exhibit none of the exclusion criteria may be enrolled. A Potential Subject Roster, which will document the initials of each patient considered for study entry, the date of assessment, severity of diagnosis and the reasons for not enrolling any potential study subject, will be maintained at each site.

## **E. Randomization**

As subjects qualify for the study, subject numbers will be assigned in strict sequential order at each site. Subjects will receive one of two treatment regimens according to a computer-generated randomization schedule prepared by the CCRP Pharmaceuticals, Inc. and kept at the individual investigational sites. This randomization schedule will provide for equal numbers of subjects in the two regimens. The random study group assignment will be provided for each subject in individually sealed envelopes. As a qualified subject enters the study, the next available randomization envelope in the sequence will be opened to reveal the appropriate therapy regimen. The following two regimens will be used:

- 1. Drug A 500 mg PO q12h**
- 2. Cefuroxime axetil 500 mg PO q12h**

Total therapy duration will be 7 to 14 days, as clinically indicated. A minimum of five days of therapy will be required for analysis of microbiologic response, unless subjects have failed clinically and have taken sufficient drug to be considered evaluable within this time. If, in the opinion of the investigator, a subject requires more than 14 days of therapy (e.g., *Legionella pneumophila*, slowly resolving pneumonia, etc.) the medical monitor should be contacted.

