## **DESCRIPTION OF STUDY**

This is a multicenter, prospective, randomized, Phase III study to evaluate the safety and efficacy of Drug A compared with cefuroxime axetil in the treatment of community-acquired pneumonia in adults.

Investigators will collectively enroll approximately 450 outpatient subjects with community-acquired pneumonia to ensure clinically evaluable data from 400 subjects. The study will be terminated when 200 clinically evaluable subjects per treatment group have been prospectively enrolled. The study may be amended if necessary to ensure enrollment of sufficient numbers of subjects with infections due to critical pathogens. The data will be pooled across investigators for safety and efficacy analyses. A subject is eligible for study entry if the infection was acquired in a community setting.

Subjects who meet all the inclusion criteria and exhibit none of the exclusion criteria may be enrolled. A Potential Subject Roster, which will document the initials of each patient considered for study entry, the date of assessment, severity of diagnosis and the reasons for not enrolling any potential study subject, will be maintained at each site. As subjects qualify for the study, subject numbers will be assigned in strict sequential order at each site. Subjects will receive one of two treatment regimens according to a computer-generated randomization schedule prepared by the CCRP Pharmaceuticals, Inc. and kept at the individual investigational sites. This randomization schedule will provide for equal numbers of subjects in the two regimens. The random study group assignment will be provided for each subject in individually sealed envelopes. As a qualified subject enters the study, the next available randomization envelope in the sequence will be opened to reveal the appropriate therapy regimen. The following two regimens will be used:

- 1. Drug A 500 mg PO q12h**
- 2. Cefuroxime axetil 500 mg PO q12h**

Total therapy duration will be 7 to 14 days, as clinically indicated. A minimum of five days of therapy will be required for analysis of microbiologic response, unless subjects have failed clinically and have taken sufficient drug to be considered evaluable within this time. If, in the opinion of the investigator, a subject requires more than 14 days of therapy (e.g., *Legionella pneumophila*, slowly resolving pneumonia, etc.) the medical monitor should be contacted.

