All subjects will be assessed for possible adverse events during the course of the study. All adverse events will be documented on the case record form. Safety will also be assessed by the physical examinations and laboratory tests performed pre-therapy and post-therapy.

Efficacy will be assessed by microbiological and clinical response. Microbiological data will be obtained from cultures of respiratory secretions.

Clinical response will be evaluated by assessing physical exam signs and symptoms, laboratory results, and chest X-ray findings by the investigator after the completion of therapy.

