### **A. Visit #1 - Baseline Visit**

At the baseline visit, the following will be performed:

1. Sign informed consent form
2. Pertinent medical history
3. Pertinent physical examination, including vital signs
4. Chest x-ray (PA & lateral)
5. Respiratory secretions must be obtained within the 48 hours prior to study entry for routine culture and Gram stain. Deep expectorated or auctioned sputum, transtracheal aspirates, bronchial brushings, washings, biopsies, or pleural fluid are

all acceptable. Specimens should also be cultured for *M pneumoniae*, *L. pneumophila*, and *C pneumoniae* when indicated and if the microbiology laboratory has the capability to perform these cultures.

Disk and MIC susceptibilities for all study drugs are to be performed on all aerobic pathogens isolated (except *M pneumoniae*, *L. pneumophila*, and *C pneumoniae*). Genus and species identification is required on all pathogens isolated.

6. Obtain venous blood samples and process blood at local institution:
  - a. Hematology:
    - hemoglobin
    - hematocrit
    - RBC
    - platelet count
    - WBC, including differential
  - b. Serum chemistry:

-glucose	-total bilirubin
-creatinine	-inorganic phosphorous
-BUN	-alkaline phosphatase
-total protein	-calcium
-albumin	-uric acid
-sodium	-chloride
-potassium	-CO 2
-SGOT	-LDH
-SGPT	
  - c. Pharmacokinetics (these will be shipped and analyzed at a central laboratory, see Appendix II for instructions)
7. Urinalysis, including pH, specific gravity, and microscopic examination of sediment for RBC, VIBC, and non-amorphous crystals
8. Urine pregnancy test
9. Evaluate subject for signs and symptoms of pneumonia
10. Complete confidential follow-up form
11. Assign subject number
12. Pharmacist to open randomization envelope and dispense/prescribe appropriate drug

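### The randomization schedule is kept at the sites with no limit on who may see it, which can defeat the sealed envelopes meant to conceal allocation

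*Protocol*

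**What the plan says.** The Protocol describes allocation twice in matching words, under Description of Study and in section 2.2, E. Randomization. In both, the schedule is prepared by the sponsor "and kept at the individual investigational sites. This randomization schedule will provide for equal numbers of subjects in the two regimens". Section E then says: "The random study group assignment will be provided for each subject in individually sealed envelopes". When a qualified subject enters, "the next available randomization envelope in the sequence will be opened to reveal the appropriate therapy regimen". Subject numbers are given out strictly in order at each site.

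The baseline visit (section V, A. Visit #1) lists assignment of the subject number as item 11, and as item 12: "Pharmacist to open randomization envelope and dispense/prescribe appropriate drug".

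The design statement reads "This is a multicenter, prospective, randomized, Phase III study to evaluate the safety and efficacy of Drug A" and has no blinding term. No matched tablets, double-dummy or blinded assessor appears anywhere in the document. Clinical response is judged from signs, symptoms, "laboratory results, and chest X-ray findings by the investigator after the completion of therapy".

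**The concern.** Sealed envelopes work only if those who decide on entry cannot learn the content of the next one by another route. A schedule held in the same building is such a route. With sequential numbering, the next subject number is always known, and a schedule that lists regimens by number gives the arm.

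What is at stake is selection at entry. Eligibility leaves room for judgement: the clinical picture must be consistent with pneumonia, the infiltrate compatible with acute infection, and subjects who meet the criteria may be enrolled, not must be. Someone who knows the next arm could delay, decline or favour a particular patient. The arms could then differ in prognosis before treatment starts. The chi-square comparison in section VIII would not reveal this, and adjustment for recorded baseline factors could not be relied on to remove it.

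**Working it through.** No figure of the Protocol is in dispute. The check is first a reading of the text and then an illustration.

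**1. Is the wording a slip?** The location of the schedule appears in the same words under Description of Study and in 2.2.E. Section VI (Study Drug Administration) also says that the sponsor prepares the schedule, but says nothing about where it is kept. No passage withdraws or narrows the statement.

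**2. What conceals the assignment?**
- Individually sealed envelopes, used in sequence (2.2.E).
- Opening when a qualified subject enters (2.2.E).
- A pharmacist opens, listed after the subject number is assigned (Visit #1, items 11 and 12).

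**3. What could undo it?**
- The schedule is at the site (2.2.E).
- No custodian is named, access is not limited to the pharmacy, and the pharmacist is not required to be independent of enrolment.
- Numbers are strictly sequential, so the position on the list is known.
- No masking is described and the envelope reveals the regimen itself, so nothing suggests that the schedule carries codes that would hide the drug.

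Steps 2 and 3 do not fit together. A person with access to the schedule has no need of the envelope and knows each next assignment.

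**4. How much could be guessed without the list?** With arms visible after allocation and a forced n:n split, a person who always guesses the arm that is behind expects this many correct guesses out of 2n:

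E = n + 2^(2n-1) / C(2n, n) - 0.5

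- *Assumed* 10:10 over 20 subjects at one site (n = 10; the Protocol Summary gives 20 subjects per site): 2^19 / C(20,10) = 524288 / 184756 = 2.84, so E = 10 + 2.84 - 0.5 = 12.34, and 12.34 / 20 = 61.7%.
- *Assumed* blocks of 4 (n = 2): 2^3 / C(4,2) = 8 / 6 = 1.33, so E = 2 + 1.33 - 0.5 = 2.83, and 2.83 / 4 = 70.8%.

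A simulation of the same two cases gave 61.7% and 70.9%. The assignments that are certain, because one arm is already used up, came to about 9% and 33%.

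The Protocol promises equal numbers in the two regimens. It states neither a 10:10 split within each site nor any block size, so these rates are illustrations and not properties of the plan.

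**The case against.** The strongest reply is that the Protocol already has most of a sound procedure: sealed envelopes, sequential use, opening only for a qualified subject, a number assigned first, and a pharmacist who opens. It also requires a Potential Subject Roster recording each patient considered, the severity, and the reasons for not enrolling, which helps to detect selective entry. And the clause about the sites may mean only that the envelopes are there, or that the pharmacy alone holds the list.

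All of this is fair, and it limits the point. A reader might infer that staff at every site can read off every next assignment. The documents do not support that: it holds only for people with access to the list, and access is left unstated. But the benign readings are not written down either. The text speaks of the schedule and names the envelopes separately. The roster records decisions after they are made and does not conceal allocation.

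A reader might also infer that biased rating of clinical response is an equal part of the defect, curable by telling the pharmacist not to disclose the arm. The lack of any described masking is a real limitation for an investigator-rated outcome, less so for culture-based eradication. But the investigator's Visit #2 includes adverse event and compliance checks, and nothing says that the tablets match. Pharmacist silence would give only partial masking; effective masking would probably need a separate assessor. Nor can a rating shift be set against the trial's precision, because section VIII gives no response rates or interval width.

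**Conclusion.** The point holds as a defect in custody of the schedule. The Protocol states in two places that the schedule is kept at the sites, relies on envelopes to conceal what that schedule contains, and does not say who may see it. As written, concealment can fail completely for anyone in enrolment who has access. This is a risk created by the wording, not evidence that bias has occurred.

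It rests on two readings: that the schedule is a document distinct from the envelopes, and that silence on masking means none is planned. The Protocol never calls the study open-label, but the revealed regimen and the absence of any masking measure make the second reading sound. The guessing rates of about 62% and 71% are not needed for the conclusion. The unmasked rating of clinical response should be acknowledged as a limitation and does not carry this point.

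**What to change.** Under Description of Study and in 2.2.E, delete the part of "prepared by the CCRP Pharmaceuticals, Inc. and kept at the individual investigational sites" that places the schedule at the sites. State instead that the sponsor's randomization office holds the schedule off site. Add that sites receive only sequentially numbered, opaque, sealed envelopes held by the pharmacist; that each is opened after eligibility and the subject number are recorded; that date, time and signature are logged; and that envelopes and log are reconciled at close-out.

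Sealing, sequential use and opening by the pharmacist are already in the Protocol. The new elements are off-site custody, opacity, pharmacist custody of the envelopes, the log and the reconciliation. The cost is a change of wording and a small amount of pharmacy logging. If the sponsor meant only that the envelopes are at the sites, the deletion costs nothing. The change should be in place before the first subject is enrolled. Rater masking is not part of the required change.

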## **V. PROCEDURES**

The schedule of study procedures is diagrammed in the Flow Chart (Appendix 1).

### **A. Visit #1 - Baseline Visit**

At the baseline visit, the following will be performed:

1. Sign informed consent form
2. Pertinent medical history
3. Pertinent physical examination, including vital signs
4. Chest x-ray (PA & lateral)
5. Respiratory secretions must be obtained within the 48 hours prior to study entry for routine culture and Gram stain. Deep expectorated or auctioned sputum, transtracheal aspirates, bronchial brushings, washings, biopsies, or pleural fluid are

all acceptable. Specimens should also be cultured for *M pneumoniae*, *L. pneumophila*, and *C pneumoniae* when indicated and if the microbiology laboratory has the capability to perform these cultures.

Disk and MIC susceptibilities for all study drugs are to be performed on all aerobic pathogens isolated (except *M pneumoniae*, *L. pneumophila*, and *C pneumoniae*). Genus and species identification is required on all pathogens isolated.

6. Obtain venous blood samples and process blood at local institution:
  - a. Hematology:
    - hemoglobin
    - hematocrit
    - RBC
    - platelet count
    - WBC, including differential
  - b. Serum chemistry:

-glucose	-total bilirubin
-creatinine	-inorganic phosphorous
-BUN	-alkaline phosphatase
-total protein	-calcium
-albumin	-uric acid
-sodium	-chloride
-potassium	-CO 2
-SGOT	-LDH
-SGPT	
  - c. Pharmacokinetics (these will be shipped and analyzed at a central laboratory, see Appendix II for instructions)
7. Urinalysis, including pH, specific gravity, and microscopic examination of sediment for RBC, VIBC, and non-amorphous crystals
8. Urine pregnancy test
9. Evaluate subject for signs and symptoms of pneumonia
10. Complete confidential follow-up form
11. Assign subject number
12. Pharmacist to open randomization envelope and dispense/prescribe appropriate drug

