**Drug A Protocol Summary**  
**Protocol No. NDP- 1 003**

- 1. Project Status:** Phase III
- 2. Purpose:** To evaluate the safety and efficacy of Drug A versus cefuroxime in the treatment of community acquired pneumonia
- 3. Design:** Multicenter, prospective, randomized Phase III study
- 4. Number of Subjects:** Approximately 450 outpatient subjects to yield 400 subjects that met the criteria, minimum of 200 subjects in each of two treatment groups. 20 subjects will be enrolled from each site
- 5. Types of Subjects:** Male and female subjects with clinical symptoms of community-acquired pneumonia who are appropriate candidates for oral therapy
- 6. Key Inclusion Criteria:** Subject must be at least 18 years old with clinical signs and symptoms of acute pneumonia
- 7. Key Exclusion Criteria:** Subjects infected with a known resistant organism; acute allergic reaction to any non-antimicrobial, or a severe reaction to penicillin or any cephalosporin; renal failure; neutropenia; pregnant or nursing mothers; prior use of an investigational agent within 30 days; or previous treatment under this protocol
- 8. Comparative Agent:** Cefuroxime axetil
- 9. Dosage & Duration:** Drug A - 500 mg PO q12h x 7-14 days Cefuroxime axetil - 500 mg PO q12h for 7-14 days
- 10. Safety Parameters:** Safety evaluations will be based on changes in the physical exam and laboratory tests from pre- to post-therapy and reporting of any adverse events.
- 11. Efficacy Parameters:**
  - a. Microbiological response (2-4 days post-therapy) will be based on eradication of the pathogens isolated at admission.
  - b. Clinical response (2-4 days post-therapy) will be based on resolution of signs/symptoms and changes in radiological findings reported at admission.
- 12. Location:** Multicenter; 20-25 sites are expected to participate
- 13. Data Analysis:**

- a. Safety - adverse events and changes in physical examinations and clinical laboratory tests from pre- to post-treatment will be summarized
- b. Efficacy- the microbiological eradication rates and clinical response rates will be compared for Drug A and Cefuroxime axetil

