**B. Visit #2 - On-Therapy Evaluations (Study Days 5-7)**

The investigator should assess the overall clinical progress of the subject and adverse events.

1. Physical exam, including vital signs
2. Evaluate subject for signs and symptoms of pneumonia
3. Assess adverse events
4. Pharmacokinetics (see Appendix II for instructions)
5. Assess drug compliance

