**C. Visit #3 - Post-Therapy Evaluation (Study Days 2-4 After Completion of Therapy)**

The investigator should assess the subject's overall clinical progress and assess adverse events.

Clinical response will be determined by comparing a subject's post-therapy signs and symptoms to those observed on admission as well as by comparing post-therapy chest x-ray findings with those on admission, as follows:

Cure:	Resolution of signs and symptoms associated with active infection along with resolution of chest x-ray findings
Improved:	Incomplete resolution of signs, symptoms, and chest x-ray findings
Failure:	No response to therapy
Unable to Evaluate:	Due to the administration of non-study antimicrobials, I insufficient course of therapy, subject not returning for post-therapy evaluation, etc.

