**D. Visit #4 - Post-Study Evaluation (Study Days 21-28 After Completion of Therapy)**

1. Physical exam, including vital signs
2. Evaluate subject for signs and symptoms of pneumonia
3. Culture and Gram stain of respiratory secretions, if still positive at Visit #3 (Study Days 2-4 After Completion of Therapy)
4. Repeat chest x-ray, if pneumonia not resolved at Visit #3 (Study Days 2-4 After Completion of Therapy)
5. Clinical response will be assessed by comparing the subject's pre-study signs and symptoms (including pre-study chest x-ray findings) to those observed post-therapy:
  - Cure - resolution of signs and symptoms associated with active infection, along with resolution of chest x-ray findings
  - Improved - continued incomplete resolution of signs and symptoms with no deterioration or relapse during the follow-up period
  - Failure - no response to therapy
  - Relapse - resolution or improvement of signs and symptoms at the post-therapy evaluation with reappearance or deterioration of signs and symptoms of infection.
  - Unable to Evaluate - due to the administration of non-study antimicrobials, subject not returning for post-study evaluation, etc.
6. Assess adverse events

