**Study Measurements and weights**

All clinical data will be collected on standardized case report forms.

The Case Report Form will be used to collect all patient data and assessments that will be used for evaluation of the patient's response to treatment. It is the responsibility of the PI to ensure the completeness and accuracy of case report forms. One set of case report forms should be completed for each subject participating in the trial. The Case Report Forms should be completed within two (2) days of the patient's visit for review by Clinical Research Monitors, Inc., CCRP Pharmaceutical's agent for monitoring the trial. Case Report Forms will be monitored following guidelines established by CCRP Pharmaceuticals at the study onset. Investigators will permit inspection of the study files and patient medical charts by authorized representatives of Clinical Research Monitors & CCRP Pharmaceuticals and responsible government agencies.

Data will be entered at the site by the Principal Investigator (PI) and/or his/her designee. After all data has been entered and all queries are resolved for a patient, the patient's data will be locked. Once the data is locked, the PI will review the patient's data and will attach an electronic signature to the e-crf indicating that he/she has reviewed all data and to the best of his/her knowledge, the data has been accurately captured. It will be necessary for the PI to have on file at the FDA a certification statement that his/her electronic signature is 'intended to be the legally binding equivalent of traditional handwritten signatures.'

All proposed publications and presentations by investigators must be submitted to CCRP Pharmaceuticals for review and approval. A copy of each proposed publication and presentation

shall be submitted at least sixty (60) days prior to submission for publication or presentation. This provision is in recognition of CCRP Pharmaceutical's rights and responsibility to provide peer input regarding the content and conclusions of such publications and to ensure that none of its confidential information will be disclosed or inappropriately utilized.

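### Use of non-study antimicrobials decides evaluability, but no listed procedure explicitly records it, and the baseline specimen is not tied to antibiotic exposure, so another drug's clearance can count as eradication

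*Protocol*

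**What the plan says.** **Where antimicrobial use matters.** Section V.C (Visit #3) lists, as the first reason for being unable to evaluate clinical response, "Due to the administration of non-study antimicrobials". Section V.D (Visit #4) gives the reasons as "due to the administration of non-study antimicrobials, subject not returning for post-study evaluation, etc". The Description of Study closes the trial once each group has 200 clinically evaluable subjects, and allows about 450 enrolled to reach 400.

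**What the visits collect.** The nearest items are "Pertinent medical history" at baseline (V.A) and "Assess drug compliance" at Visit #2 (V.B). Neither names antimicrobials. The lists for Visits #3 and #4, the early-withdrawal section (V.E) and the rows of Appendix I have no item for prior or concomitant medication. The section on study measurements says the case report form will be "used to collect all patient data and assessments that will be used for evaluation" of response, without listing its contents.

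**The baseline specimen and entry.** V.A item 5 states: "Respiratory secretions must be obtained within the 48 hours prior to study entry for routine culture and Gram stain". The only time-limited bar on earlier drugs in the exclusion criteria is "Use of an investigational agent within 30 days prior to entry into the study". According to the protocol summary, item 11, microbiological response "will be based on eradication of the pathogens isolated at admission".

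**The concern.** A fact that determines a subject's rating should have a scheduled place in the data. Here it has none that the protocol names, although the count that stops enrolment depends on it. A statistical analysis plan can define how to handle antibiotic use, but it cannot recover dates and times that were never collected.

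The specimen rule adds a second route to error. Take a subject who is cultured, is given a marketed antibiotic, and enters up to 48 hours later, still with two qualifying signs and an infiltrate. Nothing in the criteria excludes that subject. The isolate from the earlier specimen is the admission pathogen, and its later absence counts as eradication on whichever study drug was assigned. The Visit #1 signs and symptoms, against which clinical response is judged, may also be partly treated already. Both comparisons named in Section VIII are exposed.

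**Working it through.** **1. Is antimicrobial use recorded anywhere?**

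| Place | Nearest item | Names antimicrobials? |
|---|---|---|
| V.A, Visit #1 | medical history | no |
| V.B, Visit #2 | drug compliance | no |
| V.C, Visit #3 | none in the procedure list; use appears only as a reason for the rating | no collection item |
| V.D, Visit #4 | none in the procedure list; use appears only as a reason for the rating | no collection item |
| V.E, early withdrawal | repeats the Visit #3 procedures | no |
| Appendix I, 11 rows | medical history | no |
| Case report form section | general statement of scope | no |

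**2. Does any rule stop another drug's clearance from being counted?** The exclusions cover known resistant organisms, certain drug reactions, severe renal failure, neutropenia, pregnancy or nursing, investigational agents and earlier treatment under the protocol. None covers a recent or ongoing marketed antibiotic. The rule on non-study antimicrobials in V.C and V.D concerns clinical response, and does not say whether use before entry counts. For microbiological response the Description of Study sets a minimum of five days' therapy, with an exception for early clinical failure, but no condition on other antibiotics. No rule closes the gap.

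**3. The plan's own figure.** Section VIII gives alpha 0.05, 85% power and 200 per group, but no rates, difference or margin, so 200 cannot be reproduced. It can only be fitted. Assume a two-sided test and 90% in the better arm (the background section's approximate rate for Drug A):

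n = [1.960 √(2p̄(1 - p̄)) + 1.036 √(p₁(1 - p₁) + p₂(1 - p₂))]² / d²

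With p₁ = 0.900, p₂ = 0.792, p̄ = 0.846 and d = 0.108: (1.0005 + 0.5231)² / 0.011664 = 199.0, rounded up to 200. The stated size therefore fits a difference of about 10.8 points. Separately, 1 - 400/450 = 11.1% is the whole allowance for non-evaluable subjects, whatever the reason.

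**4. Size of the dilution.** Suppose a share p of each arm is pretreated and responds at the same rate r in both arms. Then

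observed difference = [(1 - p)p₁ + p r] - [(1 - p)p₂ + p r] = (1 - p)(p₁ - p₂).

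Power with n = 200 per arm = Φ{[d - 1.960 √(2p̄(1 - p̄)/n)] / √[(p₁(1 - p₁) + p₂(1 - p₂))/n]}. For power, take r = 90% and true rates of 90% and 79%.

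| p | difference if truly 10 points | diluted rates | difference if truly 11 points | power |
|---|---|---|---|---|
| 0 | 10 | 90.0 v 79.0 | 11.0 | 86% |
| 10% | 9 | 90.0 v 80.1 | 9.9 | 80% |
| 20% | 8 | 90.0 v 81.2 | 8.8 | 71% |
| 30% | 7 | 90.0 v 82.3 | 7.7 | 61% |

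Worked entries: at p = 0, (0.110 - 0.0709)/0.0358 = 1.09, and Φ(1.09) = 86%. At p = 20%, (0.088 - 0.0688)/0.0348 = 0.55, and Φ(0.55) = 71%.

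The rates, r and p are all illustrative. The power column assumes all 200 per arm contribute. The number with an admission pathogen is not given, so power for eradication cannot be stated.

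**The case against.** - **The data may be captured anyway.** The case report form is meant to hold everything used to evaluate response, and by the protocol's own rules that includes non-study antimicrobials. A medical history is taken, and monitors may inspect charts. Appendix I also omits the Visit #2 compliance check, so absence from the chart alone proves little. This stands in part. A reader might infer that use would be known only if a subject volunteered it, or that the trial could not report it; the documents do not support either, because the form is not shown. What they do support is that no listed procedure explicitly requires the record.
- **Harm at Visit #4.** A reader might infer that unrecorded antibiotics between Visits #3 and #4 turn failures or relapses into cures. Under V.D such a subject belongs in the unable-to-evaluate category, so the error would run from that category to cure. The summary places both efficacy parameters 2-4 days after therapy, before this interval, and subjects are told at Visit #3 to report returning symptoms at once. The Visit #4 issue is secondary.
- **Equal dilution does not produce a false difference.** Correct. Section VIII states a chi-square comparison with no equivalence or non-inferiority margin. A reader might infer that the trial would wrongly declare similarity. That would follow only if a non-significant result were read as similarity, which the section does not say.
- **Pretreatment should balance by randomization.** On average, yes, which is why dilution is the main effect. Use after randomization need not balance: the envelope reveals the regimen and the protocol describes no blinding. The documents do not show that it would differ by arm.

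**Conclusion.** The concern holds as a gap in data capture and in the specimen rule. Antimicrobial use governs evaluability and, through it, the count that closes enrolment, but no listed procedure explicitly requires it to be recorded. V.A item 5, read with the exclusion criteria and the definition of microbiological response, lets clearance by another drug be counted as eradication on study drug. The documents show that this can happen. They do not show that it does, or how often.

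If pretreated subjects respond alike in both arms and make up the same share p of each, the true difference shrinks to (1 - p) of its size: 10 points become 8 at p = 20% and 7 at p = 30%. Under the further assumption of 90% v 79% with 200 per arm, power falls from 86% to 71% and 61%. The consequence for the stated test is lost power and observed rates pulled together. The point should be corrected before enrolment, because the timing of antibiotics relative to culture may not be recoverable later.

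**What to change.** 1. Add an item for prior and concomitant antimicrobials (drug, start and stop date and time, reason) to Visits #1 to #4, Early Withdrawal, Appendix I and the case report form.
2. Record the date and time at which each baseline specimen was collected.
3. Amend V.A item 5 so that a baseline specimen counts for microbiological response only if no non-study antimicrobial was given between its collection and the first study dose.
4. State in V.C and V.D whether use before entry counts towards the unable-to-evaluate rating. This covers the clinical comparison, which the specimen condition does not reach.

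The cost is one more item per visit and one more flow-chart row. Some subjects will leave the microbiological comparison; how many cannot be estimated from the documents. Whether to limit prior antibiotics at entry, or to take a repeat specimen, is for the sponsor to decide, and this fix requires neither.
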